### Type 1 error control

Not applicable given that there is only one primary endpoint.

### Analysis dataset

The primary hypothesis will be tested using the per protocol dataset (refer to section 3.3 where this analysis dataset is described). Imputation of missing data in an intent to treat analysis is not deemed essential, given that the primary hypothesis is not related to making claims about the efficacy of a device, strategy or processing algorithm compared to a baseline.

There will be no missing data for the pre-operative acoustic hearing thresholds variable, since a subject inclusion criterion is a pre-operative hearing threshold of  $\leq 80$  dB HL at 500 Hz. Missing hearing threshold data at FUV in the compromised CM and/or preserved CM groups is possible. However, it is anticipated that there will be less than 5% of missing data and that any missing data will be missing at random.

### 3.2.3 Secondary Hypotheses

#### Secondary hypothesis 1

The secondary hypothesis 1 that deterioration in average low frequency post-operative hearing threshold at FUV2 in the implanted ear for subjects with intra-operative compromised CM will be greater than subjects with preserved CM, will be evaluated with a one-sided independent t-test using an alpha level of 0.05. A Mann-Whitney U test will be conducted if

---

the data is non-normally distributed. The analysis considerations will be identical to those described for the primary hypothesis in 3.2.2.

The null and alternative hypotheses are as follows:

$$H_0: CM^- - CM^+ \leq 0$$

$$H_a: CM^- - CM^+ > 0$$

where:

$CM^-$  = mean or median drop in low frequency postoperative hearing at 3 months post-activation (FUV2) for the compromised CM group.

$CM^+$  = mean or median drop in low frequency postoperative hearing at 3 months post-activation (FUV2) for the preserved CM group.

## Secondary hypothesis 2

The secondary hypothesis 2 predicting that earlier onset of CM response during electrode array insertion will be associated with better pre-operative high frequency acoustic hearing thresholds, will be tested using a Pearson Product Moment Correlation coefficient or Spearman rank correlation coefficient with a one-sided alpha level of 0.025.

The onset of the CM response will be represented by even numbers from low to high on an interval scale, with low numbers representing earlier onset. The onset of the CM response will be tracked by impedance measures that are interleaved with the ECoG recordings. As each electrode in the array enters the perilymph in the cochlea, there will be a measured sharp drop in impedance. Therefore, CM onset will be defined in terms of the  $n^{\text{th}}$  electrode (out of the 22 electrodes) to enter the cochlea. For example, CM onset might first occur when impedance sharply drops as the 14th electrode in the 22 electrode array enters the cochlea. Since the impedance measures are not smoothed and instantaneous, the CM onset scale will have precision to every 2nd electrode in order of cochlea entry. Pre-operative high frequency hearing will be defined as the average of pre-operative hearing thresholds in the implanted ear at 2 kHz, 3 kHz, and 4 kHz.

The null and alternative hypotheses are represented as follows, where  $r$  refers to the Pearson correlation coefficient.

$$H_0: r = 0$$

$$H_a: r > 0$$

If the null hypothesis of no association between CM onset and high frequency acoustic hearing is rejected, a simple linear regression will then be computed to define the predicted influence of the pre-operative acoustic hearing thresholds on the CM response characteristic.

Both the auditory hearing threshold data and the CM response data will initially be assessed for normality and if there is a significant departure from normality, the data will be transformed to better approximate normality. If the data transformation is unsuccessful, a non-parametric Spearman rank correlation will be computed. It is highly probable that the non-parametric correlation coefficient will be used when high frequency acoustic hearing is

expressed as the highest cut-off frequency at which there is measurable high frequency hearing.

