Furthermore, to inform Cochlear's future technology and product development of intra-operative monitoring tools that utilize ECoG measures, it is of interest to examine the influence of pre-operative acoustic hearing status on the characteristics of the CM response during intra-cochlear insertion of the electrode array. Understanding further the factors that influence the characteristics of the CM response (e.g. onset and latency) might enable reference markers to be incorporated within future software monitoring tools as to expected behavior of the CM response for cochlear implant recipients with varying characteristics. Additionally, it may be possible to provide reference data regarding expected responses for different electrode types. The CRT system provides the capability to interleave measures of electrode impedance with the ECoG recordings, which is expected to provide an ability to track the progressive entry of electrodes into the cochlea during insertion (through observed reduction in impedance when electrodes are in contact with perilymph). The combined use of such impedance measures and ECoG recordings will be used to characterize the CM response as a function of the number of electrode contacts inside the cochlea. Earlier CM onset is expected with better high frequency acoustic hearing, since the electrode array initially advances through the basal region of the cochlea passing the outer hair cells that are responsive to the high frequencies. Although maximum hair cell response to the 500 Hz acoustic tone occurs in the apical region the cochlea, hair cell populations in the basal region will also respond to the travelling wave. Latency change will be measured between two CM onset points and is predicted to increase as the advancing electrode passes surviving inner and outer hair cells populations. If there is no measurable high frequency hearing, it is hypothesized that CM amplitude will increase without an increase in latency as the electrode advances towards the apex.

Postoperative CRT sweeps will be conducted immediately following the wound closure (baseline) and at either 4-6 weeks post-surgery or at 3 months post-implantation. This will allow changes over time in different components of the ECoG to be characterized. The relationship between hearing threshold levels (HTLs) in the implanted ear and ECoG responses at FUV1 or FUV2 (e.g. CM and acoustic neurophonic response (ANN) thresholds) will also be examined.

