7.3.4 Intra-Operative Cochlear Response Telemetry Recording and Surgical Video

Intra-operative video recording will be obtained prior to cochlear opening and conducted during electrode insertion and until the closure of the subcutaneous/muscle layer.

After the receiver-stimulator package is positioned and secured, the transmitting coil and sound processor will be placed in a sterile sleeve or bag and subsequently the coil magnet placed in position over the implant package. Electrode conditioning will be conducted when the most apical electrode (electrode 22) is first placed into the basal turn of the cochlea, just prior to advancement of the array, or in a saline solution prior to insertion. On the stabilization of the impedance of the apical electrode, the surgeon will be informed that the insertion may commence. Intra-operative recordings obtained during electrode insertion will typically use a 500 Hz acoustic stimulus (of 6 ms duration and an inter-

stimulus interval of 70 ms) presented at 100 dB HL, with recording on the most apical electrode (electrode 22).

The surgical video will be time-stamped to the CRT recordings. This will be achieved with the surgeon clicking surgical tweezers in front of the microscope 3 times at the end of the surgery, whilst the operator records the current index on the CM monitoring trace that will be updating in real-time. The operator of the CRT software will also capture surgical events using the software time-stamped to the CM recording.

Monitoring of the CM will continue throughout the surgical procedure until closure of the deep (subcutaneous/muscle) layer.

Post-insertion measures will be obtained (after closure of the subcutaneous/muscle layer) using a frequency sweep and an electrode sweep routine.

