7.5 Subjects

7.5.1 Inclusion Criteria

- Candidate for cochlear implantation (with CI522, CI532 or Hybrid-L24 according to local indications)
- 18 years of age or older at the time of enrolment
- Pre-operative audiometric threshold in the implanted ear at 500 Hz of better than or equal to 80 dB HL
- Willingness to participate in and to comply with all requirements of the protocol

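### Secondary hypothesis 2: the unadjusted correlation tests association but cannot show that high-frequency hearing influences CM onset, because 500 Hz hearing is left out

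*SAP*

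**What the plan says.** SAP 3.2.3 (secondary hypothesis 2) predicts that "earlier onset of CM response during electrode array insertion will be associated with better pre-operative high frequency acoustic hearing thresholds". The test is a Pearson or "Spearman rank correlation coefficient with a one-sided alpha level of 0.025". The predictor is the "average of pre-operative hearing thresholds in the implanted ear at 2 kHz, 3 kHz, and 4 kHz". The outcome is the ordinal position, out of 22, of the electrode entering the cochlea when the CM first appears, resolved to every second electrode. A significant result is followed by a simple linear regression, described as defining the predicted influence of the thresholds. No covariate is named. The covariates in SAP 3.4.4 (age, gender, intraoperative steroids) are for hearing preservation only. Exploratory hypothesis 3 in SAP 3.2.4 concerns demographic and surgical factors, uses regression only if visual inspection suggests it, and does not name 500 Hz hearing.

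Protocol 7.3.4 states that "Intra-operative recordings obtained during electrode insertion will typically use a 500 Hz acoustic stimulus"; the remaining settings include "stimulus interval of 70 ms) presented at 100 dB HL, with recording on the most apical electrode (electrode 22". Nothing scales the level to the subject's own threshold. Protocol 7.5.1 requires a "Pre-operative audiometric threshold in the implanted ear at 500 Hz of better than or equal to 80 dB HL" and sets no lower limit.

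Protocol 6.2 asks whether pre-operative hearing influences onset. Protocol section 4 gives the mechanism: "Earlier CM onset is expected with better high frequency acoustic hearing, since the electrode array initially advances through the basal region of the cochlea". The same section places the maximum response to the 500 Hz tone in the apical region.

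**The concern.** The level of the tone above threshold differs between ears. At 100 dB HL it is 100 - 80 = 20 dB for an ear at the entry limit, and 100 - 40 = 60 dB for an ear with a 500 Hz threshold of 40 dB HL (an illustrative value). Protocol section 4 also expects CM amplitude to grow towards the apex in ears with no measurable high-frequency hearing, so it accepts that a CM can be recorded without a basal contribution. How early the CM becomes detectable may therefore depend on how well the ear responds at 500 Hz.

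If ears with better 500 Hz thresholds also tend to have better 2-4 kHz thresholds, onset and the 2-4 kHz mean will be positively correlated, which is the direction of the alternative hypothesis, even with no direct contribution from high-frequency hair cells. The planned analysis cannot tell the two explanations apart. At stake is the answer to the influence question in Protocol 6.2, and the use of the result in section 4 as a guide to expected CM behaviour in future monitoring software.

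**Working it through.** **The plan's own figure.** The only sizing in the documents is for the primary t-test. With a difference of 15 dB, SD 25 dB (d = 15/25 = 0.6), one-sided 0.05 and 80% power, the exact t-test calculation gives 35.04, so 36 per group (power 80.9%). Then 36 × 1.15 = 41.4 (stated 41) and 41/0.95 = 43.2 (stated 43). The plan's figures reproduce. The total is 2 × 43 = 86. Secondary hypothesis 2 has no sizing of its own.

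**Inputs for this check.**
- N: 86 × 0.95 = 81.7, about 82 subjects with an onset value (SAP 3.1 expects about 5% without a CM).
- Alpha: one-sided 0.025, critical value 1.960 (SAP 3.2.3).
- a = correlation of the 500 Hz threshold with the 2-4 kHz mean; b = correlation of the 500 Hz threshold with onset. The documents give neither, so both are assumptions shown over a range.
- The correlation of the 2-4 kHz mean with onset, given the 500 Hz threshold, is set to zero.

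**Formula.** With no direct high-frequency effect, the marginal correlation is r = a × b. The probability that the unadjusted test is significant is Φ(atanh(r) × √(N - 3) - 1.960), with √79 = 8.888.

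Example, a = b = 0.4: r = 0.16; atanh(0.16) = 0.1614; 0.1614 × 8.888 = 1.434; 1.434 - 1.960 = -0.526; Φ = 30%.

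The formula was compared with a simulation (10,000 runs, thresholds in 5 dB steps, onset on even numbers 2 to 22), which also gives the rejection rate of the partial correlation given the 500 Hz threshold.

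| a = b | r | Unadjusted, formula | Unadjusted, simulated Pearson / Spearman | Partial, simulated Pearson / Spearman |
|---|---|---|---|---|
| 0.2 | 0.04 | 5.4% | 5.8% / 5.4% | 2.6% / 2.7% |
| 0.3 | 0.09 | 12.3% | 12.0% / 11.1% | 2.6% / 2.8% |
| 0.4 | 0.16 | 30.0% | 29.0% / 27.4% | 2.6% / 3.1% |
| 0.5 | 0.25 | 62.2% | 60.9% / 57.4% | 2.8% / 3.4% |
| 0.6 | 0.36 | 91.8% | 91.2% / 88.6% | 3.5% / 4.2% |

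If a or b is zero, then r = 0 and the formula gives 2.5%. The partial tests stay near 2.5%. The small excess at 0.6 fits residual confounding from the rounding of recorded values.

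**Power cost of adjusting.** The r detectable with 80% power is tanh((1.960 + 0.842)/√79) = 0.305 unadjusted and tanh(2.802/√78) = 0.307 for the partial correlation. Now suppose a true r of 0.305 acts only through high-frequency hearing, so that b = 0.305 × a. The partial correlation is (r - ab)/√((1 - a²)(1 - b²)).
- a = 0.3: b = 0.0915, partial r = 0.292, power 76%.
- a = 0.5: b = 0.1525, partial r = 0.267, power 68%.

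**The case against.** The strongest reply is that nothing is wrong with the test. Protocol 6.4 states the null as no association and SAP 3.2.3 writes it as r = 0; an unadjusted correlation tests exactly that. A reader might infer from the table that the type I error rate is inflated from 2.5% to 30%. The documents do not support that reading: with a = b = 0.4 the marginal correlation really is 0.16, the stated null is false, and 30% is the test's power to detect it. This part of the reply stands.

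Two other strong readings also fail. A reader might take it that every ear receives an identical tone, but Protocol 7.3.4 says only that the recordings typically use this stimulus. The argument needs only that the level is not tied to the ear's threshold; a level that varied for other reasons would be a further unadjusted factor. A reader might also take the confounding as established. It is not: neither correlation is reported, no statement in the documents links a larger 500 Hz response to earlier onset, and the 80 dB HL limit narrows the range of 500 Hz thresholds and may weaken both correlations.

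It can also be said that reference data for future software are a predictive use, for which an unadjusted association is informative. That is fair as far as it goes. But Protocol 6.2 and the follow-on regression in SAP 3.2.3 speak of influence, and Protocol section 4 names a basal mechanism. For those statements the objection does not help.

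**Conclusion.** The point holds as one of interpretation. The planned test is valid for the stated association, but by itself it cannot support the conclusion that high-frequency hearing influences CM onset, because the most obvious rival explanation, hearing at the stimulus frequency, is measured and left out. The possible size runs from none (either correlation zero) through about 5% (both 0.2) and 30% (both 0.4) to 62% (both 0.5) of trials showing a significant result with no direct high-frequency effect. This rests on N = 82, approximate normality and the assumed correlations. It concerns a secondary hypothesis in a study with no pass/fail criterion, so it is a worthwhile, inexpensive improvement and does not touch the primary analysis.

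**What to change.** In SAP 3.2.3, secondary hypothesis 2:
- Keep the unadjusted Pearson or Spearman correlation at one-sided 0.025 as the test of the stated association. The protocol hypothesis then needs no change.
- Pre-specify beside it the partial correlation (same Pearson or Spearman choice) of onset with the 2-4 kHz mean, given the pre-operative 500 Hz threshold in the implanted ear.
- Include that 500 Hz threshold as a covariate in the follow-on regression.
- State that an effect will be attributed to high-frequency hearing only if the adjusted result supports it, and that a non-significant adjusted result does not exclude such an effect.

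Adjusting also for array type, and doing the same for the latency analysis (exploratory hypothesis 2 in SAP 3.2.4), are optional; the documents give less support for either.

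The cost is SAP wording. No new data are needed, since the 500 Hz threshold is required for entry. The adjusted test loses some power, and more so the more strongly the two thresholds are correlated, as shown in the working; the unadjusted test is unaffected.

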### 3.2.4 Exploratory Hypotheses

The following exploratory hypotheses shall include:

1. *Predictors of the incidence of compromised CM during cochlear implant surgery including influence of electrode type, insertion depth and surgical events*

Descriptive, proportional data will be presented to capture the incidence of the compromised CM for electrode type, electrode array insertion depth and surgical events such as inadvertent moving of the electrode array after insertion completion or during sealing of the round window.

2. *Association of pre-operative high frequency acoustic hearing thresholds with change in latency of CM during electrode array insertion*

It is predicted that greater CM latency (phase shift expressed in ms) during electrode array insertion will be associated with better pre-operative acoustic high frequency hearing thresholds, will be tested using a Pearson Product Moment Correlation coefficient or Spearman rank correlation coefficient with a one-sided alpha level of 0.025. The CM latency change will be measured between two CM onset points that are as widely spaced as possible, where a preserved CM is able to be measured as the electrode array is advanced into the cochlea (e.g. 10th electrode to enter versus the 22nd electrode). This CM onset range for the latency change measurement will be identical for all subjects. It will be selected by analysing the group CM data to 1) be sufficiently wide so that the latency measure is sensitive to the potential influence of surviving hair cell populations along the basilar membrane that respond to a range of frequencies and 2) include enough subjects to have adequate power for the primary endpoint analysis. Greater CM latency change will be represented by higher numbers. Pre-operative high frequency hearing will be defined as the average of pre-operative hearing thresholds in the implanted ear at 2 kHz, 3 kHz and 4 kHz, with lower numbers representing better high frequency hearing. Therefore, a negative correlation is predicted by the alternative hypothesis.

3. *Investigation of the influence of demographic and surgical factors on the morphology and time-course of the CM response during insertion and post-operatively.*

The CM response traces will be examined for any unusual patterns and whether such patterns appear to be associated with any factors (e.g. electrode type). If visual inspection suggests interesting associations in characterizing the CM response, regression analyses will be computed to further understand the predictive influence of the factors on the CM morphology and time-course.

4. *Investigation of the relationship of CM thresholds to postoperative HTLs in the implanted ear.*

This hypothesis will be tested using a repeated measures linear regression to examine the association between CM threshold (independent variable) and behavioural threshold (dependent variable) at FUV2. Thresholds are measured at several frequencies (e.g. 250Hz, 500Hz, 1 kHz, 2 kHz, 4 kHz) and this creates potential correlation within subjects, thus

necessitating repeated measures approach. The thresholds will be expressed in dB nHL. A test of the slope of the CM threshold term against a null hypothesis value of 1 will be performed; a value significantly greater than 1 would indicate behaviour thresholds are higher than the corresponding CM threshold. Frequency will also be examined to understand if there is an effect on the association of CM and behavioural threshold. If the assumption of normality fails based on a Shapiro-Wilk test of normality at the 0.05 level, the data will be arcsine transformed to minimise departure from normality. Descriptive statistics for the CM and behavioural thresholds, the mean (standard deviation) or median (inter-quartile range) as appropriate will be reported by frequency.

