**Investigation Schedule**

Procedure	POV1 Pre-operative	D0 Surgery	FUV1 4-6 Weeks Post-Surgery (+/- 1 week)	FUV2 3-Month Post-Activation (+/- 2 weeks)
Medical and Hearing History	X			
Otoscopy (Check for Wax Occlusion)	X	X	X	X
Cochlear Response Telemetry (CRT)		X	X (either FUV1 or FUV2)	
Audiometry & Tympanometry	X		X	X
Surgical Questionnaire		X		
Impedance Measures (Standard, 4-point, Voltogram)		X	X (either FUV1 or FUV2)	
Optional (where obtained at sites as part of routine clinical management): Imaging (MRI Pre-Operative; X-Ray or Cone Beam CT Post-Operative)	X		X	

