Implant surgery will be conducted (at D0). A video recording will be made during the surgical procedure to enable analysis of the CRT in response to specific surgical events. The video will be made via the operative microscope imaging system during the entire insertion, commencing just prior to cochlear opening and ending after closure of the deep (subcutaneous/muscle) layer. The video will be time-stamped to the CRT recordings. Measures of electrode impedance will be obtained during the surgery. At the completion of each subject's surgical procedure a questionnaire will be completed by the surgeon to document aspects of the surgical procedure (including surgical approach, administration of corticosteroids, and ease and depth of electrode insertion).

Post-operative assessment at 4-6 weeks (+/- 1 week) post-activation and 3 months (+/- 2 weeks) post-activation will be conducted, and involve a series of clinical tests including otoscopy, audiometry, tympanometry and electrode impedance assessment. At either 4-6 weeks post-surgery (+/- 1 week), or 3 months (+/- 2 weeks) post-activation, post-operative CRT will also be conducted.

If an intra-or post-operative imaging is performed as part of the routine clinical management at participating site, that data will be analyzed to provide an estimate of electrode array position.

Medical and audiological care throughout the clinical investigation, and at the conclusion of the investigation, will be as per standard clinical protocol for each investigational site, with the exception of the additional measurements taken as outlined.

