7.3.8 Post-Operative Cochlear Response Telemetry Recording

Post-insertion measures will be obtained using a frequency sweep (with recording from electrode 22 for signals with frequency 250, 500, 1000, and 2000 Hz delivered at a maximum comfortable listening level) and an electrode sweep (with recording using a 500 Hz acoustic signal presented at a maximum comfortable listening level and recording on electrodes 22, 20, 18, 16, 14, 12, 10, 8, 6, 4 and 2). The signal level (typically comprising a 12 ms duration stimulus and 50 ms inter-stimulus interval) will be controlled to ensure comfortable loudness presentation.

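### SAP exploratory item 4 ties the CM-to-hearing comparison to FUV2, but post-operative CRT is done at either FUV1 or FUV2; pair by visit and reconcile the CM-threshold measurement

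*SAP*

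**What the plan says.** SAP 3.2.4, item 4, examines the "association between CM threshold (independent variable) and behavioural threshold (dependent variable) at FUV2" by repeated measures linear regression. Thresholds are expressed in dB nHL and the slope is tested against 1. On frequencies it says: "Thresholds are measured at several frequencies (e.g. 250Hz, 500Hz, 1 kHz, 2 kHz, 4 kHz", a list given as examples.

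The protocol describes the follow-up recording in section 7.3.8:

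- a frequency sweep "with recording from electrode 22 for signals with frequency 250, 500, 1000, and 2000 Hz delivered at a maximum comfortable listening level";
- an electrode sweep, "recording using a 500 Hz acoustic signal presented at a maximum comfortable listening level";
- a signal level that "will be controlled to ensure comfortable loudness presentation".

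On timing, the CRT row of the Investigation Schedule reads "X (either FUV1 or FUV2" for the follow-up visits, and section 7.2 agrees: "At either 4-6 weeks post-surgery (+/- 1 week), or 3 months (+/- 2 weeks) post-activation, post-operative CRT will also be conducted". The same schedule places audiometry at both FUV1 and FUV2.

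Two other places refer to CM thresholds. Protocol section 4 says that the relation between hearing thresholds and ECoG responses at FUV1 or FUV2 will be examined, with CM and ANN thresholds as examples. SAP 3.2.4, item 7, plans to describe change over time in CM and ANN thresholds and amplitude.

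**The concern.** The SAP names one visit for an analysis whose predictor is collected at one of two visits. A subject whose CRT was done at FUV1 has no CM value at FUV2. The analyst must then leave that subject out or set an FUV1 CM value against FUV2 hearing. The first loses data that the study has collected. The second mixes time points that the plan itself treats as distinct: hearing at FUV1 is the primary endpoint and hearing at FUV2 a secondary one. The SAP does not say which to do, so the choice would be made after the data are seen.

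Two further gaps bear on the same item. The frequency sweep has no 4 kHz stimulus, although 4 kHz is among the SAP's examples. And a recording at one comfortable level gives an amplitude; the protocol describes no series of levels, search or criterion from which a CM threshold would be read.

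**Working it through.** The documents give no sample size, power or expected count for item 4, so there is no stated figure to reproduce. The check is a comparison of texts followed by an illustrative count.

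**Visit**

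- Hearing thresholds: measured at FUV1 and at FUV2 (Investigation Schedule; protocol 7.2).
- Post-operative CRT: one of the two visits (Investigation Schedule; protocol 7.2).
- The question as the protocol puts it: FUV1 or FUV2 (section 4).
- The analysis as the SAP puts it: FUV2 (3.2.4, item 4).

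Every subject with a post-operative CRT recording is therefore scheduled for audiometry at that same visit. The narrowing to FUV2 appears only in the SAP, without a reason.

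**Frequency**

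- SAP examples: 250, 500, 1000, 2000 and 4000 Hz (five).
- Protocol CRT sweep: 250, 500, 1000 and 2000 Hz (four).
- In both: four. Only 4 kHz is missing, and only on the CM side, because air-conduction audiometry in 7.3.1 includes 4000 Hz.

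**Level**

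Both sweeps in 7.3.8 are at a maximum comfortable listening level. Section 7.3.8 is the only description of how the follow-up CRT is recorded. Protocol section 4 and SAP items 4 and 7 presuppose CM thresholds, but none says how they are obtained.

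**Illustrative count**

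Inputs: 86 subjects (the recruitment target in the SAP Change History, V3) and a share p with CRT at FUV2. The documents do not give p, so 25% to 75% is assumed. The counts are upper limits, since every subject is taken to have a usable recording and audiogram.

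- Subjects contributing under a strict FUV2 reading = 86 × p.
- Subject-frequency pairs = subjects × 4 recorded frequencies.

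| p (assumed) | 86 × p | Subjects, about | Pairs (× 4) |
|---|---|---|---|
| 25% | 21.5 | 22 | 88 |
| 50% | 43 | 43 | 172 |
| 75% | 64.5 | 64 | 256 |

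With same-visit pairing the count does not depend on p: 86 subjects and 86 × 4 = 344 pairs.

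**The case against.** The strongest reply is that nothing here stops the analysis. The frequency list is introduced as examples, so the model can be fitted on 250 to 2000 Hz. Subjects with CRT at FUV2 can contribute even on the strict reading. The visit in item 4 may grammatically attach only to the behavioural threshold, and the item's heading speaks only of post-operative hearing. Thresholds are plainly intended, given protocol section 4 and SAP item 7. A threshold routine may be set out in the CRT user guide, which protocol 7.3.2 cites for surgical preparation and which is not among these documents. All of this stands, and it rules out several stronger readings that a reader might infer:

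- **That item 4 cannot be run, or that no CM threshold can be obtained.** The protocol's silence shows that the procedure is undescribed, not that none exists.
- **That subjects tested at FUV2 are self-selected.** The documents do not say who chooses the visit or on what grounds.
- **That the CM/ANN ratio analysis in the current SAP has the same visit problem.** That analysis is listed in protocol 7.1.4 as one that may be done, but is not among the eight items of SAP 3.2.4.
- **That CM amplitude should simply replace CM threshold.** The test of slope against 1 has meaning only when both variables are thresholds on the same dB scale. The presentation level is also set by each subject's comfort, so it may track the behavioural threshold, and adjusting for it could absorb the association under study.

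The reply does not remove the visit problem. If the visit applies only to the behavioural threshold, CM from FUV1 would be set against hearing at FUV2, which is the cross-visit pairing at issue. Nor does 7.3.8 refer to the user guide for the recording procedure; it states its own frequencies, electrodes and level.

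**Conclusion.** The concern holds in a limited form. Item 4 fixes a visit that the protocol does not require for CRT. Its literal use either excludes subjects recorded at FUV1 or pairs measures from different visits. On an assumed 25% to 75% with CRT at FUV2, about 22 to 64 of 86 subjects would contribute under the strict reading; the true share is unknown. The 4 kHz example has no CM counterpart, which is a matter of wording. The one gap that could block the analysis is the missing description of a CM threshold, and whether it does so depends on a fact that the documents do not give.

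The importance is low. The analysis is exploratory and has no stated power, and the primary and secondary conclusions are unaffected. The change is still worth making, because it settles the visit and the frequencies in advance and uses data already scheduled.

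**What to change.** 1. In SAP 3.2.4, item 4, replace the restriction to FUV2 with the behavioural threshold from the same visit as the CRT recording, and include visit as a factor in the model.
2. Limit the CM frequencies in item 4 to those in the protocol sweep: 250, 500, 1000 and 2000 Hz.
3. Reconcile protocol 7.3.8 with SAP items 4 and 7 by stating whether a post-operative CM threshold is measured. If it is, describe or cite the procedure and keep the planned regression and slope test.
4. Only if it is not, redefine the predictor and drop or rewrite the test of slope against 1.

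Steps 1 and 2 change SAP wording only: audiometry is already scheduled at both visits, so no procedure is added. Their cost is one more model term and a result that covers two time points instead of FUV2 alone. Step 3 needs a clarification in the documents. Step 4, if needed, costs more than wording, because item 4 would then answer a different question.
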